10.3.1 Statistical Analysis Data Sets

- 1)Safety analysis set (SAS): including subjects who have used the investigational drug at least once;
- 2)FAS (full analysis set): including all subjects who were randomized into the study group, who used the investigational drug at least once, and who had efficacy indicators after randomization at least once;
- 3)PPS (per-protocol set): subset of FAS, excluding subjects with serious protocol violations;

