Proportion of patients achieving perioperative platelet count goals ($\geq 80 \times 10^9 \mu \text{g/L}$ for major surgery and $\geq 50 \times 10^9 \mu \text{g/L}$ for minor surgery) without rescue therapy

3.2 secondary study endpoints

- 1)Median time to platelet count target;
- 2)Subject platelet count $\geq 50 \times 10^9 \text{L}$ maximum duration;

- 3)Subject platelet count $\geq 80 \times 10^9/L$ maximum duration;
- 4)Proportion of patients with surgical delay due to thrombocytopenia;
- 5)Proportion of patients undergoing surgery on schedule;
- 6)Incidence and severity of bleeding in patients;
- 7)Proportion of patients receiving emergency treatment;
- 8)Safety: Adverse events (AEs): include type, incidence, severity, duration, and relationship to study drug.

4 Experimental design

This is an investigator-initiated, single-arm, prospective clinical study to evaluate the efficacy and safety of hytrombopag in the treatment of thrombocytopenia occurring prior to scheduled surgery.⁹After signing the informed consent form, the patients will enter the screening period (up to 7 days) and receive oral treatment with hytrombopag after screening. The specific dosage regimen is: 7.5 mg, once daily, orally before bed on an empty stomach, lasting for up to 14 days, $PLT \geq 100 \times 10^9/L$. During oral administration of hytrombopag, when $PLT \geq 200 \times 10^9/L$, the administration was suspended and the hemogram was monitored every 7 days until $PLT < 100 \times 10^9/L$. During the treatment period, blood routine was monitored once every 3 days, $PLT \leq 30 \times 10^9/L$ or $\geq 300 \times 10^9/L$. Patients will have an end-of-treatment visit within 7 days of treatment discontinuation, followed by a 30-day safety follow-up period.

5 Management of Subjects

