10.3.2 Primary Efficacy Analysis

Logistic regression was used for the primary efficacy measure, with treatment as the variable analyzed and baseline platelet count as the covariate. The primary analysis was based on FAS, and the secondary analysis was based on PPS. Baseline platelet count was defined as the most recent measurement before dosing.

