10.3.5 Missing Data Handling

For the primary efficacy measure, if a patient has no measurement at a time point

and thereafter, the platelet count at that time point and thereafter is counted as not reaching $\geq 50 \times 10^9/L$.

10.4 sample size

The study was designed as a single-arm exploratory design. Based on previous relevant data reports, the estimated proportion of patients meeting platelet targets was 65%. Using NCSS PASS 15 (LLC. Kaysville, Utah, USA, ncss.com/software/pass) software, the two-sided 95% confidence interval (Clopper-Pearson method) for enrollment of approximately 50 subjects was (50.2%, 77.9%), and the confidence interval width was 27.7%.

11 Research Management

11.1 ethical requirements

·Ethics Committee

Prior to the start of the clinical trial, the clinical trial protocol shall be reviewed and approved by the Ethics Committee and approved by the Ethics Committee before implementation. During the clinical trial, major amendments to the clinical trial protocol, such as new impact on the safety of subjects, or amendments to the informed consent form, shall be approved by the Ethics Committee before implementation.

·Protection of rights and interests of subjects in clinical trials

The clinical investigator must explain to the subject that participation in the clinical trial is voluntary and that he/she has the right to withdraw from the trial at any time during any stage of the trial without discrimination, that his/her medical treatment and rights will not be affected in any way, and that he/she can continue to receive other effective treatment. The subject must be informed that participation in the trial and personal data in the trial are confidential. The subject must also be informed of the nature of the clinical trial, the purpose of the trial, the expected possible benefits and

the possible risks and inconveniences that may occur. Subjects were informed of alternative treatment options and their rights and obligations in accordance with the Declaration of Helsinki, so that they had sufficient time to consider participation in the trial and sign the informed consent form.

11.2 information requirements

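### The primary analysis set requires randomisation in a single-arm trial and an efficacy value afterwards, so dosed patients without one drop out of the denominator and the success rate can be biased upward

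*Protocol*

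**What the plan says.** Section 4 of the protocol describes the design: "This is an investigator-initiated, single-arm, prospective clinical study". No randomisation step appears anywhere in the document.

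Section 10.3.1 defines three analysis sets:

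- The safety set needs only exposure: "including subjects who have used the investigational drug at least once".
- The FAS takes those "who were randomized into the study group, who used the investigational drug at least once, and who had efficacy indicators after randomization".
- The per-protocol set (PPS) is a "subset of FAS, excluding subjects with serious protocol violations".

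Section 10.3.2 assigns the sets to the efficacy analyses: "The primary analysis was based on FAS, and the secondary analysis was based on PPS". The same section ties baseline to dosing: "Baseline platelet count was defined as the most recent measurement before dosing".

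For the primary measure, section 10.3.5 says that when a patient lacks a measurement at some time point "and thereafter, the platelet count at that time point and thereafter is counted as not reaching" the threshold of 50 × 10⁹/L.

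Section 10.4 gives the planned precision: the two-sided 95% Clopper-Pearson interval "for enrollment of approximately 50 subjects was (50.2%, 77.9%), and the confidence interval width was 27.7" percentage points, at an expected rate of 65%.

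**The concern.** There are two faults in one definition.

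First, the criterion does not fit the design. Taken literally, nobody qualifies for the FAS, and the period after randomisation has no start date. The protocol's own time anchor is dosing.

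Second, replacing randomised with enrolled, which is evidently what was meant, does not cure it. Membership still depends on an efficacy value obtained later. A patient who takes the drug and then provides none leaves the denominator. Section 10.3.5 points the other way, since a patient with no measurement from some time point onwards is treated as not reaching the threshold. A dosed patient with no later value at all is the extreme case of that rule. The set definition is applied first, so the rule never reaches this patient.

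The primary endpoint (section 3.1) is one proportion, reaching the platelet goal without rescue, and no comparator arm offsets a shrinking denominator. The planned secondary analysis cannot expose the effect, because the PPS lies inside the FAS. The safety set does hold every dosed patient, but the protocol assigns no efficacy analysis to it.

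**Working it through.** **Inputs from the protocol.** Expected rate 65%, about 50 subjects, two-sided 95% Clopper-Pearson interval, stated as 50.2% to 77.9% with width 27.7 points (section 10.4).

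**Inputs assumed.** The number k of dosed patients with no later efficacy value is not given; I take k = 0 to 5 of 50. Since 0.65 × 50 = 32.5 is not a whole number, I take 32 or 33 responders.

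**Step 1: reproduce the planned interval.** With x responders among n, the lower limit is the 0.025 quantile of Beta(x, n − x + 1) and the upper limit is the 0.975 quantile of Beta(x + 1, n − x). Setting x = 32.5 and n = 50 gives 50.21% to 77.94%, width 27.73 points. The stated figures are confirmed. They refer to all of about 50 enrolled subjects, not to a subset selected on later data.

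**Step 2: direction.** A patient with no later value cannot be shown to have reached the goal and would be a failure under section 10.3.5. Removing k such patients leaves x unchanged and changes the rate from x/50 to x/(50 − k). The ratio of the two is 50/(50 − k), which is never below 1: 1.000, 1.020, 1.064 and 1.111 for k = 0, 1, 3 and 5.

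**Step 3: size.** Rates with 95% Clopper-Pearson limits; shifts are in percentage points against k = 0.

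| k | n | 32 responders | Shift | 33 responders | Shift |
|---|---|---|---|---|---|
| 0 | 50 | 64.0% (49.2 to 77.1) | 0 | 66.0% (51.2 to 78.8) | 0 |
| 1 | 49 | 65.3% (50.4 to 78.3) | 1.3 | 67.3% (52.5 to 80.1) | 1.3 |
| 3 | 47 | 68.1% (52.9 to 80.9) | 4.1 | 70.2% (55.1 to 82.7) | 4.2 |
| 5 | 45 | 71.1% (55.7 to 83.6) | 7.1 | 73.3% (58.1 to 85.4) | 7.3 |

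One excluded patient costs 1.31/27.7 = 4.7% of the planned interval width. Five cost 7.11/27.7 = 25.7% (32 responders) or 7.33/27.7 = 26.5% (33 responders). The interval width stays between 27.3 and 28.0 points throughout, so the interval moves upward without widening enough to signal the loss.

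**Step 4: the same calculation from the other side.** If 65% of the patients who remain in the FAS succeed, the rate among all 50 dosed is 0.65 × (50 − k)/50. That is 63.7% for k = 1 and 58.5% for k = 5, a difference of 1.3 to 6.5 points.

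**The case against.** The best counter-argument is that very few patients, perhaps none, would be excluded. Treatment lasts at most 14 days. Blood counts are scheduled every 3 days in section 4 and every 7 days in the protocol summary and section 8; these passages disagree, but either gives early data. An end-of-treatment visit follows within 7 days of stopping, then 30 days of follow-up. The definition speaks of efficacy indicators, which may include bleeding, rescue or the surgery outcome, so a patient with any such information could stay in. A patient with one low count certainly stays in. Five of 50 would mean 10% of dosed patients with nothing recorded, which no figure in the protocol supports. At two excluded of 50 with 32 responders, the shift is 32/48 − 32/50, or 2.7 points, against a planned half-width of about 13.9. All of this stands, and it limits the size of the effect. It does not remove the effect: the protocol summary lists death, withdrawal and loss to follow-up as reasons for early termination, and the end-of-treatment visit cannot recover such patients.

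It can also be said that requiring one later value is a common convention, and that an analysis set and a missing-data rule do different jobs. That is true, and section 10.3.5 keeps its effect on patients who drop out after a first value. Here, however, the two rules treat the same kind of missingness in opposite ways, in a trial where the denominator is the whole analysis.

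A pre-dose count taken after enrolment might be said to satisfy the words, so that nobody dosed is lost. That reading is strained, because such a count measures no effect of treatment.

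Finally, an analysis plan that is not shown could add an all-dosed sensitivity analysis. That would help, but it would leave the protocol's primary set wrong.

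**Conclusion.** The point holds and should be fixed. It is certain from the text that the randomisation criterion cannot be met in this trial, whether or not anyone is excluded. It is equally clear that, on the sensible reading, the FAS can lose dosed patients who would otherwise count as failures, and that the error runs in one direction only.

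The size is not known from the protocol. Under the assumption of 0 to 5 exclusions among 50 dosed patients and 32 or 33 responders, the overstatement runs from zero to about 7 points; the low end is the more plausible given the visit schedule. With no success threshold stated, the consequence is an optimistic reported rate and lower confidence limit, and no changed decision.

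**What to change.** In section 10.3.1, define the FAS as *all enrolled subjects who received at least one dose of hytrombopag*, and delete both references to randomisation and the requirement for a later efficacy value.

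Add: *Dosed subjects with no platelet count after the first dose are counted as not having reached the target, and their number is reported.*

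One consequential edit follows in section 10.3.5. Because these subjects would now be handled there, the rule should refer to each subject's own target in the primary endpoint (80 × 10⁹/L for major surgery, 50 × 10⁹/L for minor surgery) and not to 50 alone. This only restates the endpoint already in section 3.1.

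Enrolled subjects who are never dosed still fall outside this set. Their exclusion does not depend on anything observed after treatment.

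The cost is a wording change in the protocol, carried into the analysis plan. No new data are needed, because the all-dosed population already exists as the safety set. The reported rate may come out slightly lower.

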10.3.2 Primary Efficacy Analysis

Logistic regression was used for the primary efficacy measure, with treatment as the variable analyzed and baseline platelet count as the covariate. The primary analysis was based on FAS, and the secondary analysis was based on PPS. Baseline platelet count was defined as the most recent measurement before dosing.

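### The primary analysis models a treatment effect that a single-arm trial cannot estimate, and does not plan the proportion on which the trial was sized

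*Protocol*

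**What the plan says.** The protocol's section 4 sets the design: "This is an investigator-initiated, single-arm, prospective clinical study". It gives one starting regimen for all patients and no comparator or second dose group. The primary endpoint in section 3.1 is a single proportion, "Proportion of patients achieving perioperative platelet count goals", with one platelet threshold for major and one for minor surgery, reached without rescue therapy.

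Section 10.3.2 names one method for this endpoint: "Logistic regression was used for the primary efficacy measure, with treatment as the variable analyzed and baseline platelet count as the covariate". It adds the populations: "The primary analysis was based on FAS, and the secondary analysis was based on PPS". It mentions no estimate of the proportion and no confidence interval. Section 10.2, on the statistical hypothesis, has a heading and no text.

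Section 10.4 sizes the study on precision alone. For an expected 65% it states that "the two-sided 95% confidence interval (Clopper-Pearson method) for enrollment of approximately 50 subjects was (50.2%, 77.9%)", a width of 27.7%.

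Section 10.3.1 defines the FAS as "including all subjects who were randomized into the study group, who used the investigational drug at least once", with at least one efficacy value after randomization.

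**The concern.** A regression coefficient for treatment compares patients who differ in treatment. Here nobody differs, so the coefficient named as the object of the primary analysis does not exist. The quantity that the trial was designed to estimate, the proportion of patients reaching target, is not named as an output of the primary analysis.

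The wording fits a two-arm randomized trial, and so does the FAS definition on which this analysis is to be run. That makes it unlikely that section 10.3.2 is a loose description of a workable single-arm method.

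Whoever analyses the data cannot carry out the sentence as it stands and will have to choose another estimator. If that choice is made outside the protocol, and possibly after data have been seen, the primary result is no longer prespecified. A further risk is that the leftover model intercept is converted to a percentage and reported as the response rate, which it is not.

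**Working it through.** **Inputs from the protocol.** Single arm and one regimen (section 4); binary primary endpoint (section 3.1); expected proportion 65%, n about 50, two-sided 95% Clopper-Pearson (section 10.4); model terms treatment and baseline platelet count (section 10.3.2).

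**1. The plan's own interval.** With x responders among n patients, the exact limits are beta quantiles:

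- lower = Beta(0.025; x, n − x + 1)
- upper = Beta(0.975; x + 1, n − x)

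At x = 0.65 × 50 = 32.5 and n = 50 the limits are 50.21% and 77.94%, a width of 27.73 points. This matches section 10.4. Wald (51.8% to 78.2%) and Wilson (51.1% to 76.7%) limits do not match, so the method stated there is the one that was used. The count 32.5 is a planning value only. The nearest attainable results are:

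| Responders | Proportion | Exact 95% interval | Width (points) |
|---|---|---|---|
| 32/50 | 64% | 49.2% to 77.1% | 27.9 |
| 33/50 | 66% | 51.2% to 78.8% | 27.6 |

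**2. The model in section 10.3.2.** As written it is

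logit P(response) = β₀ + β₁ × treatment + β₂ × baseline.

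With treatment = 1 for every patient this becomes

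logit P(response) = (β₀ + β₁) + β₂ × baseline.

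Only the sum β₀ + β₁ and the slope β₂ can be identified. Numerically, the design matrix for n = 50 has 3 columns and rank 2. More patients would not change this.

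**3. What is left once the redundant column is dropped.** An intercept and a baseline slope remain. The intercept is the log-odds of response at a platelet count of zero or, if baseline is centred, at the mean baseline count. Neither is the overall proportion. To illustrate, assume a true overall rate of 65% and normally distributed baseline counts with mean 40 and SD 18 × 10⁹/L. The mean, the SD and the slopes are assumptions; the protocol gives only the eligibility ceiling of 75 × 10⁹/L. For each slope the intercept was set so that the overall rate is 65% and then converted to a probability:

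| Log-odds slope per 10⁹/L | Intercept as a rate, uncentred | Intercept as a rate, centred |
|---|---|---|
| 0.02 | 46% | 65% |
| 0.04 | 29% | 67% |
| 0.06 | 16% | 68% |
| 0.08 | 9% | 70% |

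For slope 0.04, for example, the centred intercept is 0.690. Then 1/(1 + e^−0.690) = 66.6%. Uncentred it is 0.690 − 0.04 × 40 = −0.910, which gives 28.7%.

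**The case against.** The strongest reply accepts that the treatment term is not estimable and disputes the consequences.

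- **The proportion is planned elsewhere.** Section 3.1 defines the endpoint as a proportion, section 10.4 names an exact interval for it, and section 10.1 leaves details to a SAP that is not at hand. It is fair that an exact interval is implied. But section 10.4 is a precision calculation, and section 10.3.2, which states the primary analysis, does not carry it forward. The SAP argument would answer a missing detail. It does not answer a stated method that contradicts the design: a SAP that follows the sentence cannot run it, and one that replaces it departs from the protocol.
- **The harm is small.** An exploratory single-arm study has no comparative effect to report, no test or power depends on the model, software would usually drop or flag the duplicated column, and the proportion can be computed from the same data. A maximum-likelihood logistic model with an intercept also has a mean fitted probability equal to the observed proportion, so the model does not itself distort the rate. All of this is correct. It means that the error can be repaired, not that the plan as written yields the primary result.
- **The intercept figures are hypothetical.** They are. Nothing in the protocol proposes reporting the intercept, and the inputs are assumed. They show the size of one possible misreading, and the finding does not rest on them.
- **Correcting section 10.3.2 alone is not enough.** This stands. Read literally, no patient in this trial meets the FAS definition in section 10.3.1, so a proportion on the FAS would have no denominator. That definition has to be corrected too.

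**Conclusion.** The concern holds. The only primary analysis that the protocol states targets a treatment coefficient that a single-arm trial cannot estimate (rank 2 of 3 columns). That result follows from the design alone, with no outside assumption. Section 10.3.2 also fails to name the proportion and exact interval that sections 3.1 and 10.4 lead the reader to expect, although section 10.4 implies them.

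The sample size is not affected: the planned interval of 50.2% to 77.9% at 65% of 50 reproduces and can serve as the primary analysis. How far a reported result could go wrong depends on what the analyst substitutes. The 9% to 70% range for a converted intercept applies only under the assumed baseline distribution and slopes. This must be corrected before analysis.

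**What to change.** Replace the first two sentences of section 10.3.2 with text such as: *The primary endpoint will be summarised as the number and proportion of responders in the FAS, with a two-sided 95% Clopper-Pearson confidence interval. The same summary in the PPS is supportive.* Remove treatment as an analysed variable. If a logistic regression is kept, label it exploratory, with response modelled on baseline platelet count only. The definition of baseline in the same section can stay.

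In section 10.3.1, remove the references to randomization from the FAS definition and restate it in terms of enrolment and dosing, so that the primary proportion has a clear denominator. Carry the same wording into the SAP.

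The cost is a wording amendment to the protocol, and to the SAP if one has been written. No extra patients, visits or data are needed, and the sample size of about 50 stands.

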10.3.3 Secondary Efficacy Analyses

10.3.4 Safety analysis

Adverse events occurring during the trial will be coded using MedDRA dictionary based on safety analysis set. Frequency and incidence of adverse events will be described according to system organ class (SOC) and preferred term (PT). Correlation and seriousness of adverse events will be further tabulated. Other safety indicators will be summarized by descriptive statistics. Adverse events, adverse reactions, adverse events leading to withdrawal from the trial, adverse events leading to death, Incidence rate of serious adverse events; incidence rate calculated by subsystem and symptoms/signs (count of cases: number of subjects who have experienced at least one adverse event); severity of adverse events and adverse reactions: the same adverse event occurs multiple times in the same subject, and the most serious adverse event is included in the analysis; different adverse events occur in the same subject, and the most serious adverse event is included in the analysis.

Laboratory test parameters: Descriptive summaries of laboratory test values focused on outliers.

Vital signs: Mean, maximum, minimum, median, standard deviation are used to describe the measured values and changes at each visit.

Physical examination, 12-lead ECG, etc. were analyzed descriptively.

10.3.5 Missing Data Handling

For the primary efficacy measure, if a patient has no measurement at a time point

and thereafter, the platelet count at that time point and thereafter is counted as not reaching $\geq 50 \times 10^9/L$.

10.4 sample size

The study was designed as a single-arm exploratory design. Based on previous relevant data reports, the estimated proportion of patients meeting platelet targets was 65%. Using NCSS PASS 15 (LLC. Kaysville, Utah, USA, ncss.com/software/pass) software, the two-sided 95% confidence interval (Clopper-Pearson method) for enrollment of approximately 50 subjects was (50.2%, 77.9%), and the confidence interval width was 27.7%.

11 Research Management

11.1 ethical requirements

·Ethics Committee

Prior to the start of the clinical trial, the clinical trial protocol shall be reviewed and approved by the Ethics Committee and approved by the Ethics Committee before implementation. During the clinical trial, major amendments to the clinical trial protocol, such as new impact on the safety of subjects, or amendments to the informed consent form, shall be approved by the Ethics Committee before implementation.

·Protection of rights and interests of subjects in clinical trials

The clinical investigator must explain to the subject that participation in the clinical trial is voluntary and that he/she has the right to withdraw from the trial at any time during any stage of the trial without discrimination, that his/her medical treatment and rights will not be affected in any way, and that he/she can continue to receive other effective treatment. The subject must be informed that participation in the trial and personal data in the trial are confidential. The subject must also be informed of the nature of the clinical trial, the purpose of the trial, the expected possible benefits and

the possible risks and inconveniences that may occur. Subjects were informed of alternative treatment options and their rights and obligations in accordance with the Declaration of Helsinki, so that they had sufficient time to consider participation in the trial and sign the informed consent form.

11.2 information requirements

